Recruitment, Study Participants, and Procedures- Our target sample size is up to 150 Hispanic smokers. We will coordinate with the safety managers of the participating construction sites to identify smokers who are interested in quitting smoking and arrange a visit to meet these workers. On day 1, two bilingual PH graduate assistants will approach these workers during their break to explain the study, complete the screening, and then obtain the consent form from those who are eligible. To participate in the study participant should be Hispanic male construction workers on site who are \geq 18 year old and have smoked \geq 5 cigarettes/day in the past year. Additionally, potential participants need to be available on site in the following two days, have access to telephone, have no plans to move in the next six months, and be interested in making a serious quit attempt in the next 30 days, and have no contraindication to NRT. Exhaled carbon monoxide levels and saliva cotinine will be tested among eligible participants to verify the self-reported smoking status. Individuals who decline to participate or who are ineligible (e.g., non-Hispanics, women) will be referred to the QL and provided with brochures that include information about the QL contact number and services. They will also be given a flyer about the UM Quitville smoking cessation study for which they may be eligible (only for English speakers). Those who are potentially eligible and interested in participating in the study will sign a consent form, then undergo a baseline screening to confirm eligibility and to collect information about: demographics, job characteristics, acculturation,⁴¹ smoking history, nicotine dependence,⁴² stages of change,⁴³ quit ladder,⁴⁴ smoking self-efficacy,⁴⁵ depression,⁴⁶ social support,⁴⁷ exposure to secondhand smoke, and quality of life. All questionnaires, informed consent, and educational materials will be available in English and Spanish and will be administrated by the bilingual graduate assistants. After completing the baseline assessment, a second visit in the following day will be scheduled to provide the intervention. If time does not permit to complete the entire baseline assessment, the exhaled carbon monoxide and saliva cotinine test, demographics and smoking behavior questions will be administered on-site and the remainder will be given to the

STUDY PROTOCOL AND ANALYSIS PLAN

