Sample Size: Major goals of this pilot study are to explore acceptability of our intervention. These data also will help us to estimate the intervention’s effect size to help determine sample size needs for a future full-scale RCT. We will follow the general rule of thumb and recruit at least 126 participants (63 per group) to estimate the parameters. We will use a two-group comparison of proportions at the two-tailed alpha level and assume that the intra-cluster correlation will be low (0.01). This sample size will allow us to detect a 22% difference between the two groups (a moderate effect size of 0.46) at the two-tailed 0.05 alpha with 80% power. Expecting 20% attrition rate this will leave us with a sample of 51 subjects per group. We will, however, include all randomized participants in assessment of endpoints. We realize limitations of using pilot data to power subsequent studies, related to the inherent imprecision of estimates with small sample sizes. It is important to note, though, that our sample size is large enough to estimate the effect with a reasonably tight confidence interval, and we will not rely exclusively on this effect to estimate power, but will also make use of the extant literature.

6) Data and Specimen Banking*

The following self-reported measures will be obtained specifically for research purposes. These data will be stored in stored on a password-protected computer accessed only by approved study personnel.

- i. Demographic Data and Work Characteristics: This will include: Age, ethnicity, native borne, non native born, acculturation, income, education, health insurance status, and job activities.
- ii. Fagerstrom Test for Nicotine Dependence (FTND): All participants will be given the FTND to assess nicotine dependence. This instrument has been widely tested and used in smoking studies.
- iii. Tobacco Use History: This will include: age when the participant began smoking, number of years as a smoker, the number of cigarettes smoked per day, whether the participant had made a quit attempt in the last year, the number of past year quit attempts, and the number of last year successful quit attempts (defined as being quit for at least one month).

STUDY PROTOCOL AND ANALYSIS PLAN

- iv. Depressive Symptomatology: will be assessed with the Center for Epidemiologic Studies Depression Scale (CES-D; Radloff, 1977; Thomas et al., 2001).

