Quality Assurance- Our research team is well versed in quality assurance processes for intervention studies.^{44,45,59} Following the strategy suggested by Sechrest,⁶⁹ evaluation of any treatment program should involve satisfactory answers to three questions: 1) was the intervention both standardized and delivered as intended to the participant? 2) if so, did the participants receive it? and 3) if so, was the intervention efficacious in changing behavior? Sechrest's 3rd question involves the evaluation of outcomes, which is outlined in the Data Analysis section below. However, Sechrest's 1st and 2nd questions address treatment implementation issues. To ensure standardization of intervention content and delivery, we will use standardized treatment manuals/procedures developed particularly for this study. Participants will respond to a brief questionnaire at baseline and the 3- and 6- month follow-up to assess whether key points were learned, including the techniques and information discussed in the intervention sessions. Standard procedures will be used for instrument development, protocol and forms, and data management (e.g. entry, reconciliation, updating, and data security and confidentiality). Additionally, we will audiotape a random sample of 10% of counseling sessions for review and feedback. Participants will be asked for permission to audiotape these selected sessions as part of the consent process.

Data Analysis

The analyses of the outcomes were mainly descriptive. Chi-square tests and between-group t-tests were used to compare between-group differences in baseline characteristics, and indices of treatment implementation, adherence, and retention. Intra-class correlation coefficients were used to adjust for clustering within sites.⁵⁵ This adjustment accounted for within-site clustering of workers characteristics at each of the 17 participating sites in the trial. Chi-square tests were used to compare cessation rates in the two arms. Analyses were performed on an intention-to-treat basis, with individuals with missing outcome data or self-reported abstinence not confirmed by eCO at 6-month follow-up classified as not quit. Logistic regression analyses were conducted to assess baseline predictors of prolonged abstinence at 6-months.

8) Risks to Subjects*

Potential risks and adverse effects of the study medication will be explained to each participant when informed consent is obtained. Each participant will be instructed to

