To avoid intervention contamination within participating construction worksites, the RCT design will be a two-group cluster randomized design with seven sites per group. Our resources for this R21 allow seven subjects per group. We assume that the intra-cluster correlation will be low (0.01). We will use a two-group comparison of proportions at the two-tailed alpha level. Assuming that 10%-15% of the control group and 25% of the intervention group respond to the intervention, we will have 23% power to detect a 10% difference and 50% power to detect a 15% difference. To achieve 80% power

STUDY PROTOCOL AND ANALYSIS PLAN

for a 10% and 15% difference under the same assumptions would require sample sizes of 64 and 16 subjects per site, respectively.

12) Confidentiality

Participant names will be replaced with ID numbers and a key linking the two will be kept separate from other data and accessed only by Drs. [name] and [name]. Survey data will be stored on Dropbox and accessible only by approved study personnel. Survey data from the RCT will be stored and managed in REDCap. These data will be stored for the duration of the study protocol and until all data analysis is complete and manuscripts have been published.

13) Provisions to Protect the Privacy Interests of Subjects

Participants will interact with only a limited number of approved study personnel and will be assured that their personal information will be kept private, will be used only for research purposes, and will not be accessible to non-study personnel.

14) Consent Process

Verbal consent will first be obtained after potential participants are screened on site. Those who verbally consent will then sign a written consent before the intervention begins. Because we are recruiting Hispanic participants the consent documents will be available in both English and Spanish.

STUDY PROTOCOL AND ANALYSIS PLAN

References

1. [name] DJ, Fleming LE, Arheart KL, et al. Smoking rate trends in U.S. occupational groups: the 1987 to 2004 National Health Interview Survey. *J Occup Environ Med.* Jan 2007;49(1):75-81.
2. [name] DJ, Fleming LE, McCollister KE, et al. Healthcare provider smoking cessation advice among US worker groups. *Tob Control.* Oct 2007;16(5):325-328.

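### The sample size section promises a tight confidence interval for the effect, but the plan's own inputs give a 95% half-width of about 14 points around an expected difference of 10 to 15 points

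*Combined protocol and SAP*

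**What the plan says.** The Sample Size paragraph of section 5 (Procedures Involved) plans to "recruit at least 126 participants (63 per group) to estimate the parameters", assumes an intra-cluster correlation of 0.01, and gives 80% power for a 22-point difference. It says that the pilot data will help to estimate the effect size, and so help to determine the size of a later full-scale trial. It concedes that small samples give imprecise estimates, then answers that concession by saying that "our sample size is large enough to estimate the effect with a reasonably tight confidence interval". The same sentence adds that the pilot effect will not be the only basis for later power calculations and that published literature will also be used. No interval width, and no calculation behind the claim, appears anywhere in the document.

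The only abstinence rates are in section 11 (Local Number of Subjects), for seven sites per group: "Assuming that 10%-15% of the control group and 25% of the intervention group respond to the intervention". That section goes on: "we will have 23% power to detect a 10% difference and 50% power to detect a 15% difference".

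On the efficacy comparison, the Data Analysis part of section 7 says: "Chi-square tests were used to compare cessation rates in the two arms". It describes the analyses as mainly descriptive and mentions an adjustment for clustering by site. It specifies no between-arm estimate with a confidence interval.

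**The concern.** The plan states a precision property without a number, and the number can be worked out from the plan's own inputs. If the interval is about as wide on each side as the expected difference, the wording tells whoever designs the next trial that the pilot estimate is firmer than it is. Informing that design is one of the stated uses of the sample. The claim also depends on an interval that the analysis section does not commit to producing.

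**Working it through.** **Inputs.** From the Sample Size paragraph: 63 per arm, intra-cluster correlation 0.01, two-sided 5% level, 22-point detectable difference, all randomized participants included. From section 11: seven sites per arm, control 10% to 15%, intervention 25%. From section 5 (recruitment) and section 11: enrolment up to 150, so 75 per arm if split equally.

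**The plan's own figures first.** No width is stated, so there is none to reproduce; the power figures can be checked (two proportions, pooled variance under the null).
- 63 per arm, 22 points, control rate taken as 15% (15% vs 37%): power 81.1% ignoring clustering and 78.0% with the design effect below. The stated 80% is reproduced at that control rate.
- Section 11's 23% and 50% are reproduced as 23.3% and 49.8% at 49 per arm without a design effect, reading its sample as seven subjects at each of seven sites.

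**Design effect.** 63/7 = 9 per site, so 1 + (9 − 1) × 0.01 = 1.08.

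**Half-width.** 1.96 × √{[p₁(1 − p₁) + p₂(1 − p₂)] × DE / n}

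At 63 per arm:
- 15% vs 25%: √[(0.1275 + 0.1875) × 1.08/63] = 0.0735; × 1.96 = 14.4 points. Difference 10, interval −4.4 to +24.4.
- 10% vs 25%: √[(0.0900 + 0.1875) × 1.08/63] = 0.0690; × 1.96 = 13.5 points. Difference 15, interval +1.5 to +28.5.

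**Sensitivity.**

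| Setting | 15% vs 25% | 10% vs 25% |
|---|---|---|
| 63 per arm, no clustering | ±13.9 | ±13.0 |
| 63 per arm, DE 1.08 | ±14.4 | ±13.5 |
| 63 per arm, DE 1.08, t on 12 df (2.179) | ±16.0 | ±15.0 |
| 75 per arm, DE 1.097 (75/7 = 10.7 per site) | ±13.3 | ±12.5 |

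The 12 degrees of freedom are for 14 sites. The Data Analysis section refers to 17 sites; with 15 degrees of freedom and 126/17 = 7.4 per site the half-widths are 15.5 and 14.6. Newcombe intervals at 63 per arm, ignoring clustering, are −4.1 to +23.7 and +1.6 to +28.0, so the normal approximation is not driving the result.

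**At the 22-point difference.** The Sample Size paragraph gives no control rate, so two are assumed.
- 15% vs 37%: √[(0.1275 + 0.2331) × 1.08/63] = 0.0786; half-width 15.4 points, interval +6.6 to +37.4.
- 25% vs 47%: √[(0.1875 + 0.2491) × 1.08/63] = 0.0865; half-width 17.0 points, interval +5.0 to +39.0.

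**What the width means for sizing a later trial.** Per arm, n = (1.960 + 0.842)² × [p₁(1 − p₁) + p₂(1 − p₂)]/d², 80% power, before clustering, control 15%. Differences inside the interval −4.4 to +24.4 imply about 50 per arm (24 points), 247 (10 points), 903 (5 points), or no finite number (zero or below).

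**The case against.** The plan is more careful than the disputed phrase suggests. It promises only that the data will help to estimate the effect, concedes imprecision just before the claim, and says straight after it that the effect will not be used alone. A reader might infer that the pilot cannot supply the effect size it promises. The documents do not support that: no such promise is made, and the pilot will give an estimate, though a wide one.

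A reader might also generalise the range from slight harm to more than twice the expected benefit. That fits only 15% vs 25%. At 10% vs 25% the interval excludes zero and its upper end is 28.5/15 = 1.9 times the expected difference. At 22 points the half-width is clearly smaller than the difference and harm is excluded, although the interval is no narrower in absolute terms.

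Nor is it right that the analysis yields no effect estimate. The efficacy outcome is defined as a difference in abstinence rates, and the two arm rates give that difference. What is missing is a specified interval.

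Finally, the documents set no threshold for tightness, the 10 to 15 point difference comes from a different section than the claim, and the main outcomes are feasibility and acceptability, which are unaffected. All of this stands, and it limits the point. It does not rescue the phrase, which is offered as the answer to the plan's own concession of imprecision and has no figure behind it.

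**Conclusion.** The concern holds in a limited form. At 63 per arm the expected 95% half-width is about 13.5 to 14.4 points (15.0 to 16.0 with t on 12 degrees of freedom), and about 12.5 to 13.3 at 75 per arm. That is roughly as large as the 10 to 15 point difference assumed in section 11. At the 22-point difference it is about 15 to 17 points. The estimate is therefore too imprecise to size a full-scale trial by itself. That conclusion fits the plan's caveats; the claim of tightness does not.

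The result rests on the plan's intra-cluster correlation of 0.01, equal site sizes, the rates in section 11 and, for the 22-point case, an assumed control rate of 15% or 25%. How the later trial should be sized is a decision for that trial's protocol and is not part of this point.

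**What to change.** 1. In the Sample Size paragraph, replace the claim of tightness with the expected figure. For example: with 63 per arm and an intra-cluster correlation of 0.01, the 95% confidence interval for the difference in abstinence is expected to extend about 14 points either side of the estimate (about 13 with 75 per arm), and further with cluster-level degrees of freedom. Keep the existing caveats, which then follow naturally.
2. In the Data Analysis section, make the efficacy result the risk difference in 6-month abstinence with a site-adjusted 95% confidence interval, instead of relying on the chi-square p-value.

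Cost: the stated precision looks less favourable, and there is a little more analysis work. No extra data are needed.

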The objective of this study is to develop a brief, culturally sensitive face-to-face smoking cessation intervention for Hispanic construction workers and conduct a pilot two-arm, cluster-randomized clinical trial (RCT) to test the developed intervention for acceptability and potential efficacy- A two-arm, cluster-randomized controlled trial will be conducted with at least 14 construction sites (dependent on how many smokers can be recruited from each site), selected from one Construction Company in south Florida. Cluster randomization is used with construction site chosen as the unit of allocation because it is most practical in this setting and minimizes the risk of spillover effects from the intervention to the control group. Computer-generated random selection will be used to randomize construction sites. Then, construction sites will be randomly assigned to the intervention (enhanced care) or the control group (usual care), and study participants working in these sites will receive treatment accordingly. In conjunction with the site safety manager, we will recruit at least 126 adult Hispanic construction workers who smoke ≥ 5 cigarettes/day. Participants in the enhanced care will receive one culturally adapted brief face-to-face behavioral counseling session developed in phase 1 and delivered during breaks, two brief follow-up phone counseling calls, fax referral to the Florida quitline (QL), and provision of up to 8 weeks of free NRT. Participants in the usual care will receive fax referral to the Florida QL, and provision of up to 8 weeks of free NRT. *Main outcomes* include: 1) estimating yield (number of workers available divided by number eligible; and number eligible divided by number randomized), 2) facilitators and barriers to delivering the intervention in the proposed setting, 3) willingness of participants to be randomized and acceptability of the intervention, 4) follow-up rates, response rates to questionnaires, adherence/compliance rates, and the time needed to collect and analyze data, 5) QL enrollment rates, and 6) exploring the willingness of the target population in involving in the research design and conduct. *Potential efficacy* outcomes include the difference in prolonged abstinence, and point-prevalence abstinence rates at 6-month follow up confirmed by saliva cotinine $< 15\text{ng/ml}$.

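### Sites are randomized, but the only between-arm test named for cessation is a chi-square, and the stated clustering adjustment does not clearly reach it

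*Combined protocol and SAP*

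**What the plan says.** The opening objectives paragraph states that "Cluster randomization is used with construction site chosen as the unit of allocation". Section 5 (Design) and section 11 (Local Number of Subjects) repeat the site-randomized design.

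The Data Analysis text in section 7 runs in this order:

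- It opens with "The analyses of the outcomes were mainly descriptive".
- It names chi-square and t-tests for baseline characteristics and for implementation, adherence and retention.
- It says "Intra-class correlation coefficients were used to adjust for clustering within sites", and then "This adjustment accounted for within-site clustering of workers characteristics at each of the 17 participating sites in the trial".
- Only after that does it say "Chi-square tests were used to compare cessation rates in the two arms".
- The one regression named is a logistic model for baseline predictors of prolonged abstinence. It is not presented as the comparison of arms.

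Section 5 (Sample Size) assumes an ICC of 0.01. It says the data will help estimate the intervention's "effect size to help determine sample size needs for a future full-scale RCT", and claims that "our sample size is large enough to estimate the effect with a reasonably tight confidence interval". It adds that later power calculations will not rest on this estimate alone.

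**The concern.** When whole sites are allocated, two workers on the same site carry less independent information than two workers on different sites. A plain chi-square ignores this. The observed difference in quit rates is unchanged, but its standard error is too small. A normal or chi-square reference also takes no account of how few sites there are: 17 sites in two arms leave 15 degrees of freedom.

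The ICC sentence sits after the baseline and implementation comparisons and before the cessation test, and the sentence explaining it speaks of worker characteristics. That phrase could name the variables that were adjusted, or the reason why outcomes cluster. A plain chi-square for cessation is therefore the natural reading, though not a certain one.

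At stake is the precision attached to the abstinence difference, which is meant to feed the planning of a full-scale trial.

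**Working it through.** **Inputs from the documents.** 126 participants (63 per arm) up to 150; at least 14 sites planned and 17 in the Data Analysis text; ICC 0.01; quit rates of 10% to 15% (control) and 25% (intervention) from section 11; two-sided alpha 0.05. **Assumed here:** an ICC of 0.05 as an upper comparison, a 63/63 split, and the site sizes used in the simulation.

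**1. The plan's own power figures.** Section 11 states 23% and 50% power. Its text says seven subjects per group, but the figures fit seven per site, or 49 per arm. The design effect is DE = 1 + (7 − 1) × 0.01 = 1.06, so the effective n is 49/1.06 = 46.2 per arm.

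- 15% v 25%: SE = √[(0.1275 + 0.1875)/46.2] = 0.0826; 0.10/0.0826 − 1.96 = −0.75; power 22.7%.
- 10% v 25%: SE = √[(0.0900 + 0.1875)/46.2] = 0.0775; 0.15/0.0775 − 1.96 = −0.02; power 49.0%.

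Both reproduce. A pooled-variance formula with no design effect gives 23.3% and 49.8%, so these figures do not show how clustering was handled.

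**2. Alpha of an unadjusted chi-square.** With m = participants/sites, DE = 1 + (m − 1) × ICC and alpha = 2 × [1 − Φ(1.960/√DE)].

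| Participants / sites | m | DE, ICC 0.01 | alpha | DE, ICC 0.05 | alpha |
|---|---|---|---|---|---|
| 126 / 17 | 7.41 | 1.064 | 0.057 | 1.321 | 0.088 |
| 126 / 14 | 9.00 | 1.080 | 0.059 | 1.400 | 0.098 |
| 150 / 17 | 8.82 | 1.078 | 0.059 | 1.391 | 0.097 |
| 150 / 14 | 10.71 | 1.097 | 0.061 | 1.486 | 0.108 |

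**3. Simulation check.** Beta-binomial data, 40,000 replicates, 17 sites split 8/9, common quit rates of 12.5% and 20%. Near-equal sites (ten of 7, seven of 8) give 0.056 at ICC 0.01 and 0.086 to 0.088 at 0.05. Uneven sites (2 to 19 workers, total 126) give 0.060 to 0.061 and 0.102 to 0.104.

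**4. Interval width, 126 participants and 17 sites, ICC 0.01.** √DE = √1.064 = 1.032. The ratio t(15)/z is 2.131/1.960 = 1.087. The product is 1.122: about 3% from clustering and 9% from the t reference. The plan names no interval for abstinence, so the comparator is an ordinary Wald interval.

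**5. Worked contrasts, 63 per arm, DE 1.064.** p-values use the pooled SE and intervals the unpooled SE. For 10% v 25%: z = 0.15/√(2 × 0.175 × 0.825/63) = 2.216, and z/√DE = 2.148. The unpooled SE is 0.0664, so the half-width is 1.96 × 0.0664 = 13.0 points, or 13.0 × 1.122 = 14.6 site-aware.

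| Contrast | p, naive | p, DE only | p, DE and t(15) | Naive 95% CI (points) | Site-aware 95% CI |
|---|---|---|---|---|---|
| 10% v 25% | 0.027 | 0.032 | 0.048 | 2.0 to 28.0 | 0.4 to 29.6 |
| 6/63 v 16/63 | 0.019 | 0.023 | 0.038 | 2.9 to 28.8 | 1.3 to 30.4 |
| 15% v 25% | 0.161 | 0.174 | 0.194 | −3.9 to 23.9 | −5.5 to 25.5 |

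No contrast changes sides of 0.05.

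**6. If the chi-square was in fact ICC-adjusted.** With the ICC estimated from the data, the same simulation at ICC 0.01 and 0.05 gives alpha 0.042 to 0.058 when negative estimates are set to zero, and 0.064 to 0.093 when they are left negative.

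**7. What the trial can say about the ICC.** The large-sample SE of an ICC near 0.01 is about 0.054, so 0.01 + 1.96 × 0.054 ≈ 0.12. These data cannot rule out 0.05.

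**The case against.** The strongest reply is that the matter is already handled. The ICC sentence carries no restriction, the next one refers to all 17 sites, and the authors plainly had clustering in mind when they set the planning ICC. On that reading the cessation sentence did not need to repeat it, and step 6 shows that an ICC-adjusted chi-square with a zero floor roughly holds its level. Adjusting with the fixed planning value also holds it if 0.01 is right (simulated alpha 0.047 to 0.050), though less well if the true ICC is 0.05 (0.079 to 0.085). This stands, and it makes the concern conditional.

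It is also fair that the inflation at the plan's own ICC is about one percentage point, that the larger figures rest on an assumed ICC, and that most of the interval widening comes from the t reference rather than from clustering itself.

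The wording still does not establish that cessation was covered. A site-aware analysis of the randomized comparison is the sound default and is cheap to carry out.

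A reader might go further and infer that the plan ignores clustering altogether. The documents do not support that: they state an ICC adjustment in the analysis and assume an ICC in the planning.

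**Conclusion.** The point holds, conditionally and at modest size. If cessation was compared with a plain chi-square, the nominal 5% test runs at about 5.7% to 6.1% under the plan's ICC and about 9% to 11% under an assumed 0.05, and the interval for the difference is about 12% too narrow relative to a site-aware one at 126 participants and 17 sites. The closed-form figures assume equal site sizes; the uneven-site simulation is close to them.

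The consequences are limited. Yield, acceptability, follow-up and adherence are the main outcomes, and abstinence is labelled potential efficacy. It would be too strong to conclude that the cessation comparison is invalid or that its result would reverse: the point estimate is unaffected and none of the three worked contrasts changes its verdict. What is affected is the stated precision.

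**What to change.** Unless the ICC adjustment already covered cessation with negative estimates set to zero, analyse both 6-month abstinence outcomes (prolonged and point-prevalence) by a method that accounts for site. Use a participant-weighted risk difference with site-clustered (GEE-type) standard errors, a small-sample correction and a t reference with 17 − 2 = 15 degrees of freedom. Report the risk difference with its 95% confidence interval, and the abstinence ICC with its uncertainty. Because the section is written in the past tense, this means rerunning the comparison, not only rewording it.

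An unweighted t-test on site quit proportions is suitable only if site sizes are near equal. With uneven sites it estimates a difference of site averages rather than the participant-level difference, and its simulated power for 10% v 25% at ICC 0.01 is 39%, against 59% for the unadjusted chi-square.

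**Cost.** If cessation was already adjusted in that way, a sentence saying so. Otherwise, a short reanalysis of existing data, with wider intervals and larger p-values. For 10% v 25% at ICC 0.01, nominal power falls from roughly 60% to 52% to 55%. Part of that 60% comes from the inflated alpha, and the exact loss depends on the small-sample correction chosen; a stricter one costs more.
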